8.4. Pre-treatment Assessments

The following baseline pre-treatment assessments should be conducted after consent to participate in FAST-Forward Boost, unless they are part of standard of care, and before first treatment of radiotherapy:

- Medical history (including specific risk factors for cardiovascular disease and radiotherapy toxicity).
- Weight and height measurement.
- Breast assessment (trial-specific as used in previous trials and Harvard-Harris scale).
- Lung toxicity assessment (RTOG).
- UK only: Demographic questionnaire completed by patient (including ethnic group, sex and gender, sexual orientation and caring responsibilities)
- Pre-treatment patient-reported outcomes (e)(PRO) health-related quality of life questionnaire booklet*(not mandatory), including:
 - EORTC QLQ-C30 and QLQ-BR23
 - Body Image Scale (BIS)
 - Fatigue (EORTC QLQ FA12)
 - EQ-5D-5L
 - Radiotherapy symptoms (breast & arm/shoulder trial specific, used in previous trials)
 - *For patients receiving treatment to IMC: oesophageal toxicity (PRO-CTCAE V5.0).*
- One blood sample (not mandatory) for those patients providing consent, ideally before radiotherapy starts but can be at any timepoint. If the patient is participating in the early-side effects substudy, see box below.

Additional pre-treatment assessments for EARLY SIDE-EFFECTS SUB-STUDY ONLY

- Health care professional (HCP) assessed skin, breast and oesophageal toxicity assessment (CTCAE V5.0)
- Patients should be given the substudy specific pre-treatment (e)PRO booklet*, containing the following additional questionnaires:

- Patient assessed skin, breast, and oesophageal toxicity assessment (PRO-CTCAE V5.0 and trial specific questions as used in previous trials).
- Patient reported outcome Hospital and Anxiety Depression Scale (HADS)
- For patients who have consented to the translational substudy and early side effects translational substudy, the 1st blood sample **must** be taken **prior to** and as close as possible to the start of radiotherapy treatment.

*NB: Ideally, pre-treatment PRO questionnaires should be completed prior to the patient being aware of treatment allocation. If using ePRO, all questionnaires will be provided electronically by the ICR-CTSU office.

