Acute lung toxicity is a specific consideration relevant to patients receiving radiotherapy to the IMC (expected to be 10-15% of recruited patients). As such, a powered subgroup analysis to evaluate this is planned. Based on RTOG assessment, the rate of $\geq G3$ pneumonitis occurring up to 3 months post-treatment in patients requiring radiotherapy to the IMC is anticipated to be 2% in the control group and we want to rule out an increase of 3% (to 5%) or more in the test groups. The two test groups will be combined for this analysis since the mean dose to the lung for both schedules is almost identical. Using an A'Hern single stage design with 90% power and a 5% one-sided significance level, 311 participants receiving IMC radiotherapy in either of the experimental arms would allow a rate $> 5\%$ to be ruled out. Rates of pneumonitis in control arm patients requiring IMC radiotherapy will be considered for the purpose of confirming the design assumptions but this will be a non-comparative analysis. If more than 9/311 cases of $\geq G3$ pneumonitis were reported in those receiving 5Fr SIB, then it would not be possible to exclude a rate of 5% or more.

Sample size for late normal tissue effects analysis.

Late normal tissue effects, and particularly breast induration, are important secondary endpoints of the trial. An analysis of clinician-assessed breast induration at 3 years is planned with the aim of demonstrating that there is not an unacceptable increase in risk of these symptoms associated with either of the test schedules. Based on IMPORT HIGH(6), we expect 11% of patients to have moderate/mark clinician-assessed breast induration by 3 years in the control group. A sample size of 823 patients per arm will provide 90% power to rule out an increase of 5% (to 16%) or more in either of the test groups (2.5% alpha for each pairwise comparison). This analysis will be based on the per protocol population. Allowing for approximately 20% of patients missing the relevant assessment data (or excluded from the per protocol population), the anticipated timing of this analysis is when 3090 patients have reached 3 years follow-up after randomisation.

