10.3. Endpoint Definitions

Primary endpoint

The primary endpoint is ipsilateral breast tumour recurrence at 5 years, defined as either invasive or non-invasive ipsilateral tumour recurrence in the breast, including tumours considered to be new primaries by virtue of biology or location. Kaplan-Meier estimation will be used, with observations censored at death or most recent follow-up assessment for those patients without an event.

Secondary endpoints

- Patient-reported acute radiotherapy adverse effects (up to 3 months post-treatment*), with a focus on skin, breast, and oesophageal toxicity (PRO-CTCAE v5.0 and trial-specific assessments).
- Patient-reported late effects (between 1- and 5-years post-treatment*), with a focus on breast and arm/shoulder symptoms, using both standard instruments (EORTC QLQ BR-23) and trial-specific assessments.
- Patient-reported fatigue and quality of life (EORTC QLQ FA12, QLQ C30, QLQ BR-23, Body Image Scale (BIS), EQ5D-5L), measured throughout follow-up.
- Clinician-reported acute skin and oesophageal toxicity (CTCAE v5.0, up to 7 weeks post-treatment*) and breast oedema (trial specific, used in previous trials).
- Clinician-reported lung toxicity (RTOG, 3- and 12-months post-treatment*).
- Clinician-reported late normal tissue effects and cosmetic outcome (between 1- and 5-years post-treatment*), assessed with tools developed in previous breast radiotherapy trials and the Harvard Harris scale.

- Clinician-reported other late radiotherapy adverse events (between 1- and 5-years post-treatment*), including arm and breast lymphoedema, sensori-motor symptoms, symptomatic rib fracture, symptomatic lung fibrosis and ischaemic heart disease.
- Recurrence-free survival, defined as time to the first of: invasive ipsilateral breast tumour recurrence, invasive loco-regional recurrence, distant recurrence or death from any cause. Observations will be censored at most recent follow-up assessment for those patients without an event.
- Breast cancer-related survival, defined as time to breast cancer death. Observations will be censored at death due to other cause or most recent follow-up in those patients without an event.
- Overall survival, defined as time to death from any cause, with observations censored at most recent follow-up for surviving patients.
- Cost-effectiveness, based on health economic analysis which incorporates data on patient-reported health resource usage and health status (EQ-5D-5L).

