The primary endpoint will be presented by trial arm using Kaplan-Meier curves; estimated 5-year event rates will be given along with 95% confidence intervals. The treatment effect from each pairwise comparison will be presented as an absolute difference, by applying the hazard ratio (and corresponding 95% confidence interval) to the control group 5-year event-free estimate. This will be the primary assessment of non-inferiority (whether or not the upper limit of the confidence interval exceeds 2%). Additionally, the hazard ratio will be used to present treatment effect on a relative scale, presented with a 95% confidence interval. Hazard ratios will be derived from Cox proportional hazard regression models. The primary analysis will be unadjusted, but estimates will also be presented after adjustment for factors used in the randomisation algorithm and other important prognostic factors (which will be pre-specified in the analysis plan). As noted above, a sensitivity analysis based on a per protocol population will also be reported. The proportional hazards assumption will be checked and, if violated, appropriate alternative methods will be applied.

Analysis of secondary endpoints

PRO questionnaires will be scored using published manuals, including methods for handling missing data. Analyses of both patient-reported and clinician-reported toxicity data will follow methods established in previous breast radiotherapy trials(6, 10, 16, 39, 40) (11) and will account for multiple testing by adjustment of significance levels. Frequencies of early and late toxicities will be summarised at each time point/period and compared between treatment groups using chi-squared test or Fisher's exact test as appropriate. Where appropriate, longitudinal models (e.g. generalised estimating equations) including all assessments over follow-up, and survival analyses of time to first moderate/marked adverse effect will be carried out with comparisons between treatment groups, adjusting for balancing and other factors (for example, pre-treatment HADS score) where relevant. Event rates at key time points will be reported with 95% confidence intervals. For the analysis of late radiation effects on normal tissues the two test groups will be compared to estimate by interpolation the 5Fr schedule equivalent to control in terms of adverse effects.

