Measures used for all participants

- EORTC QLQ-C30 is a 30-item cancer quality of life-specific instrument, which comprises 5 functional sub-scales, 2 symptom subscales and additional symptom items and questions about global health and global quality of life.(61)
- EORTC QLQ-BR23 breast cancer module is a 23-item scale designed for use in breast cancer patients. It incorporates five multi-item scales to assess systemic therapy side effects, breast symptoms, arm symptoms, body image and sexual functioning. In addition, single items assess sexual enjoyment, hair loss and future perspective.(62)
- 10-item Body Image Scale (BIS) (of which 4 items are already incorporated in the BR23) was designed for use with cancer patients and has been widely used in national breast cancer treatment trials. (63)
- EORTC QLQ FA12 is a 12-item scale on fatigue which will be used in this trial to provide detailed data to assess the short- and longer-term impact of radiotherapy.(64)
- Protocol-specific items to assess radiotherapy symptoms as used in previous breast radiotherapy trials: 13 items specific to post-radiotherapy breast symptoms and shoulder/arm functioning. These include change in skin appearance, change in overall appearance of the breast, breast shrinkage and hardening, position of the nipple, difficulty getting a bra to fit, shoulder stiffness, experience of pins and needles in arm, numbness on fingers, weakness on arms or hands.

Please refer to appendix A3 for details of additional questionnaires that will be used to inform health economics analysis.

Measures used in the early side effects sub-study

In addition, the first 115 patients recruited into each arm of the trial will take part in the early side-effects sub-study and will complete the following questionnaires:

- PRO-CTCAE v5.0 items relating to acute toxicities in skin, breast, and oesophagus
- Trial specific questions: 4-items specific to any acute symptoms in the treated breast: skin reddening, skin blistering, breast swelling and breast pain or tenderness during and immediately after radiotherapy.
- Hospital Anxiety and Depression Scale (HADS)(65) will measure psychological distress. HADS has been widely used in clinical trials to date and provides clinically interpretable outcomes. This is not a trial endpoint itself but will be assessed pre-treatment and used to support interpretation of the other patient-reported outcome data.

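### The pre-treatment breast grade is due in every participant but has no stated role in the crude late-effect comparisons or in the time-to-first-event definition; using it would be a nearly free improvement

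*Protocol*

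**What the plan says.** Section 8.4 lists, among the pre-treatment assessments for all participants, "Breast assessment (trial-specific as used in previous trials and Harvard-Harris scale". Section 8.7 describes the breast assessment in the same terms at years 1, 3 and 5.

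Section 10.3 defines the endpoint as "Clinician-reported late normal tissue effects and cosmetic outcome (between 1- and 5-years post-treatment", timed from the start of treatment. It does not require the effect to be new since the pre-treatment assessment.

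Section 10.1 sizes one late-effect analysis, clinician-assessed induration at 3 years: "we expect 11% of patients to have moderate/mark clinician-assessed breast induration by 3 years in the control group". It continues: "A sample size of 823 patients per arm will provide 90% power to rule out an increase of 5% (to 16%) or more" in either test group, with "2.5% alpha for each pairwise comparison".

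Section 10.4 compares toxicity frequencies at each time point by chi-squared or Fisher's exact test. Where appropriate it adds longitudinal models, and "survival analyses of time to first moderate/marked adverse effect will be carried out with comparisons between treatment groups". That sentence goes on to allow adjustment for the balancing factors and for other factors where relevant, with the pre-treatment HADS score as its example. HADS is collected only in the early side-effects sub-study. Appendix A2 says "the first 115 patients recruited into each arm of the trial will take part in the early side-effects sub-study", which is about 345 of 4830 participants.

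**The concern.** Every participant has had breast-conserving surgery, in some cases mammoplasty or perforator-flap reconstruction, before the pre-treatment assessment. Some breasts may therefore already be graded moderate or marked before the first fraction. A chi-squared or Fisher test has no place for a baseline grade. A time to first moderate or marked effect with no condition on baseline turns such a patient into an event at the year 1 visit, whichever schedule was given.

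Randomisation spreads these patients evenly on average, so they create no false difference. They do add variance, and they leave fewer patients in whom a new effect can occur, so a true excess looks smaller. The 3-year induration analysis seeks to rule out an excess, and there shrinkage favours passing. Section 10.4 intends early publication of that analysis as safety reassurance. Section 1.1 says that toxicity will decide between 30Gy and 31Gy if both are non-inferior for recurrence.

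The one baseline covariate given as an example is missing by design in about 93% of participants (1 − 345/4830). The more relevant one is due in all of them.

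**Working it through.** **Inputs from section 10.1.** Control rate 11%, margin 5 points, power 90%, alpha 2.5% per comparison (taken as one-sided), 823 per arm, about 20% missing or excluded, 3090 patients in total.

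**The plan's own figure.** For a difference of two proportions that are truly equal:

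n = (1.96 + 1.2816)² × 2 × 0.11 × 0.89 / 0.05² = 822.9, so 823 per arm.

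823 / 0.80 = 1028.75, so 1029 per arm and 3087 in three arms, against 3090 stated. Both figures reproduce. The design is an unadjusted two-proportion comparison with no baseline term.

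**Assumption.** Let b be the proportion already moderate or marked before radiotherapy, equal in all arms and persisting to year 3. The protocol does not give b, so 1%, 3% and 5% are used for illustration. New induration in the remaining patients differs by a true 5 points.

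**Dilution.** The excess seen over all patients is 5 × (1 − b) points.

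**Error against a 5-point margin for new induration.** Error = Φ((0.05 − seen excess)/SE − 1.96), with SE = √([p_c(1 − p_c) + p_t(1 − p_t)]/823). The 11% can be read in two ways:

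- Total induration, including baseline cases: p_c = 0.11 and p_t = 0.11 + 0.05(1 − b).
- New induration only: p_c = b + (1 − b) × 0.11 and p_t = b + (1 − b) × 0.16.

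**Power when the arms are equal.** Power = Φ(0.05/√(2p_c(1 − p_c)/823) − 1.96).

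| b | Excess seen | Error, 11% total | Error, 11% new only | Control rate, 11% new only | Power, 11% new only |
|---|---|---|---|---|---|
| 0% | 5.00 | 2.5% | 2.5% | 11.0% | 90.0% |
| 1% | 4.95 | 2.7% | 2.7% | 11.9% | 88.0% |
| 3% | 4.85 | 3.1% | 3.0% | 13.7% | 84.0% |
| 5% | 4.75 | 3.5% | 3.4% | 15.5% | 80.1% |

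Example at b = 5%, new only: rates 0.1545 and 0.2020, SE = 0.01883, and error = Φ(0.0025/0.01883 − 1.96) = Φ(−1.827) = 3.4%. Power = Φ(0.05/0.01782 − 1.96) = Φ(0.846) = 80.1%. If 11% is total, power stays at 90%.

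**Which remedy removes the dilution?** A baseline-adjusted risk difference standardised over all patients still targets 5 × (1 − b) points and only narrows the interval. With baseline cases treated as certain events in both arms, SE = (1 − b) × √([0.11 × 0.89 + 0.16 × 0.84]/(823(1 − b))). Error is then 2.7%, 3.1% and 3.5% at b = 1%, 3% and 5%, no better than the crude test.

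Restricting to patients not already moderate or marked brings the target back to 5 points and the error to 2.5%. It leaves 823(1 − b) = 815, 798 or 782 per arm. Power is 91.8%, 95.3% or 98.2% if 11% is total, because the new-case rate is then lower. It is 89.7%, 89.1% or 88.5% if 11% is new cases only.

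**The case against.** The strongest reply is that the protocol does not exclude the baseline grade. The modelling sentence in 10.4 admits further covariates, and its example is itself a pre-treatment score. Surgery type, including perforator-flap reconstruction, is a stratification factor under 10.2, so part of the surgical contribution is covered by the balancing factors. Covariate lists and event definitions are normally left to the SAP, and 10.4 also refers to the methods of earlier breast radiotherapy trials. All of this stands. A reader might infer that the plan ignores baseline; the document does not show that. The adjustment clause does not reach the chi-squared and Fisher comparisons, however, and it does not alter what counts as a first event.

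Second, section 10.1 puts the margin on patients who have induration by 3 years. On that quantity the error is 2.5% as designed. The higher figures arise only if the margin is meant for new induration. This also stands.

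Third, the prevalence is assumed, and high values fit the protocol poorly. At b = 10% the new-only reading gives a control rate of 0.10 + 0.90 × 0.11 = 19.9% at 3 years. Section 1.1 reports 10.6% at 5 years for the same 48Gy schedule in the earlier boost trial. The total reading would leave only (0.11 − 0.10)/0.90 = 1.1% new induration. The range is therefore held to 5%.

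Last, the protocol does not list the items graded before treatment. That induration is among them is inferred from the matching descriptions in 8.4 and 8.7.

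**Conclusion.** This is a free improvement, not an error in a stated figure and not a contradiction between sections. As written, the crude comparisons and the first-event definition make no use of a baseline grade that the trial already plans to collect in everyone.

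The consequence is dilution and noise, never a spurious difference. It is small at a prevalence of 1% (error 2.7%, power 88% at worst) and material at 5% (error about 3.4% to 3.5%, power 80% if 11% is new cases only). These figures rest on an assumed prevalence that is equal across arms and persists to year 3, on induration being graded before treatment, and on a margin read as new induration.

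Two stronger readings should be avoided. Cosmesis is not subject to the 5-point margin, which covers only clinician-assessed induration at 3 years. Nor is the 823-per-arm design underpowered or anti-conservative for total induration, the quantity that section 10.1 appears to describe.

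**What to change.** In section 10.4, or in the SAP with a pointer from 10.4:

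- Adjust the late-effect models, including the 3-year induration analysis, for the same item's pre-treatment grade. Name that grade in place of, or beside, the HADS example.
- Count as a first event only a moderate or marked grade that is worse than the patient's pre-treatment grade.
- For the 5-point margin, add an analysis limited to patients not already moderate or marked before radiotherapy. A difference standardised over all patients does not remove the dilution.
- Keep the crude frequencies at each time point alongside.

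In section 10.1, state whether the 11% control rate is total or new induration.

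The cost is a little more analysis, a rule for missing pre-treatment grades, and a slightly smaller restricted set (782 to 815 per arm at the assumed prevalences). No visit or assessment is added.

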10.5. Interim Analyses and Stopping Rules

An Independent Data Monitoring Committee (IDMC) will be formed and will confidentially review accumulating safety and efficacy data from the trial at regular intervals (at least annually). Given the non-inferiority hypothesis, and that primary endpoint events will accrue slowly relative to recruitment timescales, early stopping on the basis of efficacy is not expected to be relevant and so no formal interim analysis or

stopping rules are in place. However, at each review, the IDMC will consider the balance of risks and benefits in the accumulating data, as well as any emerging external evidence, in making recommendations to the TSC regarding continuation of the trial.

At the time of analysis for the Early Side-Effects Sub-Study, if 6 or more participants (out of 103) within either test group have skin reactions \geq grade 3 (on CTCAE v5.0) then it would not be possible to exclude a 10% rate and this will provide stopping guidelines on which the IDMC will base their recommendations. PRO-CTCAE v5.0 data will also be considered. Similarly, for the subgroup analysis of IMC patients, 9 or more cases of RTOG \geq grade 3 pneumonitis in the first 311 IMC patients receiving 5Fr SIB (either test group) would mean a 5% rate could not be excluded and provides stopping guidelines on which the IDMC will base their recommendations. In both cases, consideration will also be given to the observed control arm rates for these toxicities and whether these align with design assumptions. Unless the IDMC advise otherwise, recruitment will continue whilst these analyses are undertaken.

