3. TRIAL DESIGN

FAST-Forward Boost is a phase III, multi-centre, randomised controlled trial. The patient population is people with a diagnosis of breast cancer treated with breast conserving surgery who are recommended radiotherapy which includes a boost dose to the tumour bed. This includes people who need radiotherapy to nodes (level 1-4 axilla, +/- IMC) in addition to radiotherapy to the breast. A total of 4830 patients will be included.

Patients will be treated using standard radiotherapy to the breast +/- nodes with a SIB to the tumour bed and randomised on a 1:1:1 basis to one of the following schedules:

- Standard radiotherapy to the breast +/- nodes using a schedule of 40Gy/15Fr over 3 weeks with a 48Gy/15Fr simultaneous integrated boost (SIB) of the tumour bed (**Control Group**)
- 26Gy/5Fr over 1 week with a 31Gy/5Fr SIB (**Test Group 1**)
- 26Gy/5Fr over 1 week with a 30Gy/5Fr SIB (**Test Group 2**)

Patients requiring nodal boosts will be eligible for inclusion if they also require a tumour bed boost. The nodal boost will be 48Gy/15Fr if randomised to the control group and 30Gy/5Fr if randomised to either of the test groups.

The trial will provide a robust assessment of the test interventions and, in addition to evaluating tumour recurrences rates (primary endpoint with a non-inferiority hypothesis), will assess toxicity in both the short and longer term (considering both patient and clinician perspectives), as well as health economic consequences and long-term disease outcomes.

The trial includes an Early Side-Effects Sub-Study which will provide an early safety review whilst recruitment is ongoing. The trial will initially open at selected sites who can take part in this sub-study which will include the first 345 patients (approximately) recruited at those sites. Both clinician and patient-reported acute toxicity will be assessed, with a focus on acute skin reactions. In particular, the sub-study is powered to exclude a 10% or greater rate of CTCAE v5.0 skin reactions \geq grade 3 in either of the test arms. Once recruitment to this sub-study is complete then the trial will open to recruitment at further sites.

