An assessment of acute toxicity (clinician- and patient-reported skin, breast and oesophageal symptoms measured using CTCAE v5.0 and PRO-CTCAE v5.0) will be performed with the aim of identifying any early safety signal with either of the test schedules. The primary endpoint for this analysis, on which the sample size is based, is clinician-reported CTCAE v5.0 skin toxicity. Grade ≥ 3 acute skin reactions are expected to be low, about 3% in the control group. The aim of this analysis will be to rule out $\geq 10\%$ acute skin reactions CTCAE v5.0 grade ≥ 3 in either test group. Based on an A'Hern single-stage design with 90% power and 5% one-sided significance level, this would require 103 participants in each of the test groups. The same number of patients will be included from the control group to confirm the design assumptions, but this will be a non-comparative analysis. Allowing for approximately 10% of patients missing the relevant assessment data (or excluded from the per protocol population on which this analysis will be based), approximately 345 patients will be included in this sub-study. If 6/103 or more participants within either test group have CTCAE v5.0 skin reactions \geq grade 3 then it would not be possible to exclude a 10% rate.

Sample size for subgroup analysis of pneumonitis rates in IMC population.

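### The skin-toxicity guideline is read only at the full sub-study analysis, although the sixth evaluable event already fixes its answer, and further sites may open before that analysis exists

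*Protocol*

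**What the plan says.** Protocol section 10.1 sizes the early side-effects sub-study on clinician-graded CTCAE v5.0 skin toxicity. Reactions of grade 3 or worse are the target: "acute skin reactions are expected to be low, about 3% in the control group", with 10% as the rate to rule out. "Based on an A'Hern single-stage design with 90% power and 5% one-sided significance level", "this would require 103 participants in each of the test groups". About 10% is added for missing data or exclusion from the per-protocol set, giving about 345 patients, or 115 per group.

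Section 10.5 turns the cut-off into guidance for the IDMC: "At the time of analysis for the Early Side-Effects Sub-Study, if 6 or more participants (out of 103) within either test group have skin reactions" of grade 3 or worse, "then it would not be possible to exclude a 10% rate and this will provide stopping guidelines". Section 10.4 ties that analysis to 103 patients in each test group with CTCAE data. PRO-CTCAE data and the observed control-arm rate are weighed alongside.

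Two statements set what happens meanwhile. Section 3: "Once recruitment to this sub-study is complete then the trial will open to recruitment at further sites". Section 10.5: "Unless the IDMC advise otherwise, recruitment will continue whilst these analyses are undertaken". The IDMC sees accumulating safety data at least annually, and 10.5 says that no formal interim analysis or stopping rules are in place.

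**The concern.** The sub-study exists to give an early safety review, but its one numerical criterion is consulted only after the last evaluable patient has been treated and followed. If a test group had a real excess of severe skin reactions, the criterion could be met well before then, and nothing in the protocol requires anyone to be told.

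Meanwhile the trial may expand. Week 7 from the start of radiotherapy is the last in-person skin grading (section 8.6), and radiotherapy starts ideally within 4 weeks of randomisation (section 8.12). The last sub-study patient's final grading may therefore come about 4 + 7 = 11 weeks after the moment at which further sites may open.

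At the new sites there is no weekly in-person CTCAE skin grading and no sub-study adverse event reporting (sections 8.6 and 9.2). Serious adverse event (SAE) reporting covers everyone, but a grade 3 skin reaction is not automatically serious (section 9.1). Skin changes are also listed as expected (section 9.4), so they would not take the expedited route for unexpected events (section 9.6).

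**Working it through.** **1. The plan's own figure.** Inputs from section 10.1: acceptable rate 3%, rate to exclude 10%, one-sided 5%, power 90%. An exact binomial search for the smallest n and c with P(X ≤ c | 10%) ≤ 0.05 and P(X ≤ c | 3%) ≥ 0.90 gives n = 103 and c = 5:

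- P(X ≤ 5 of 103 | 10%) = 0.0479
- P(X ≤ 5 of 103 | 3%) = 0.9099

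So six or more is the right cut-off. The total also reproduces: 3 × 103 = 309, and 309 / 0.9 = 344, stated as about 345.

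**2. Does the sixth event settle the rule?** The number of evaluable events cannot fall, so reaching six at any point up to 103 is the same event as having six or more at 103. Alpha (0.048) and power (0.910) are unchanged if the count is watched as it grows. If all 115 in a group were evaluable, P(X ≤ 6 of 115 | 10%) = 0.0513, still above 0.05. Six events therefore fail to exclude 10% for any n from 103 to 115.

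**3. When does the sixth event come?** Its position follows the negative binomial distribution, here conditional on occurring within 103 patients. The documents give 10%; the higher rates are assumptions shown as a range. For the last column, assume 115 per group over 9 months (39 weeks), which is 2.95 per week. Detection takes 7 weeks from entry if radiotherapy starts at once and 11 weeks if it starts 4 weeks later, so about 21 to 32 patients enter before the event is seen.

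| True rate | P(six reached by 103) | Median patient at sixth event | Of 115, still to come | Of those, entered after detection |
|---|---|---|---|---|
| 10% | 0.952 | 56 | 59 | 27 to 38 |
| 15% | 0.999 | 38 | 77 | 45 to 56 |
| 20% | 1.000 | 29 | 86 | 54 to 65 |
| 30% | 1.000 | 19 | 96 | 64 to 75 |

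**4. Entry after expansion.** Take the 7 weeks (1.6 months) after sub-study recruitment closes, both test groups combined:

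- At the sub-study's own rate: 345 / 9 = 38.3 per month; × 2/3 = 25.6; × 1.6 = about 41.
- At the average later rate (3.5 years is 42 months, less 9): (4830 − 345) / 33 = 136 per month; × 2/3 = 91; × 1.6 = about 145. This is an upper figure, because sites open gradually.

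**5. Could expansion precede any review?** The green target in section 10.6 is more than 350 participants at 9 months after opening. At that pace all 345 are recruited before 12 months, so an annual review counted from opening need not fall first.

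**6. False alarms.** At a true 3% rate the chance of reaching six is 1 − 0.910 = 9.0% per group, and 1 − (1 − 0.0901)² = 17% for at least one of the two. This is the same as at the single planned look.

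**The case against.** Sections 3, 10.1, 10.4 and 10.5 agree with one another, and continuing recruitment during the analysis is a stated choice. There is no contradiction here and no error in the boundary. That stands: the point concerns only when a correct rule is read.

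The IDMC may act sooner. Section 10.5 has it review safety at regular intervals, section 11.3 lets it release side-effect data at any stage, and its charter is not shown and may provide for closer review. Annual is a minimum. Under amber recruitment (101 to 350 by month 9), or if the year is counted from an earlier start, a review could fall before expansion. This limits the point but does not remove it, because the protocol permits early review without requiring it.

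A reader might infer that a sixth event shows excess harm or obliges the trial to stop. The documents do not support that. Six of 103 is 5.8%; crossing means only that 10% cannot be excluded, and the guideline is advisory. The analysis is also per protocol, so an event in a patient later excluded would not count.

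A reader might also take all 86 patients still to come at a 20% rate as avoidable, or 145 as the number in one group. The first ignores the time needed to see the event; the second covers both test groups at the full later rate.

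Nor are patients outside the sub-study unobserved. SAEs in all patients are reported within 24 hours of the site's becoming aware, up to 30 days after the last fraction (section 9.3). Non-serious grade 3 reactions are what this misses. Finally, the protocol does not anticipate a signal and cites a registry of 383 patients on similar five-fraction boosts with no grade 3 events.

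**Conclusion.** The point holds as a weakness in timing. The protocol applies a correct boundary later than its own logic needs, and links site expansion to completed recruitment rather than to the result. Once a sixth evaluable grade 3 or worse reaction occurs in a test group, further patients cannot restore the ability to exclude 10%.

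The size depends on the unknown true rate. At 10%, about 27 to 38 further sub-study patients would enter the affected group after the boundary was observably reached; at an assumed 20%, about 54 to 65. In the 7 weeks after expansion, about 41 to at most about 145 would enter the two test groups combined. These figures assume even accrual of 345 in 9 months, the median position of the sixth event, and 7 to 11 weeks to detection. That no review falls before expansion further assumes green-target recruitment and only the guaranteed annual meeting.

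**What to change.** In section 10.5, state that the IDMC is notified when the sixth evaluable grade 3 or worse CTCAE skin reaction is recorded in either test group, rather than only at the planned analysis, and require prompt eCRF entry of these grades. In section 3, state that the running count per test group is given to the IDMC when further sites are to open.

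Threshold, sample size, error rates and the IDMC's discretion over any recommendation stay as they are, and no stopping or treatment rule is added. The cost is a sentence in each section, prompt entry of one eCRF item, and a possible unscheduled IDMC review (about 9% per group if the true rate is 3%).
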